6.1. General Principles

All data processing, summarization and analyses will be performed using Fortrea's SAS Environment / Version 9.4 (or later) of the SAS® statistical software package.

The default summary statistics for quantitative variables will be the number of observations (n), mean, standard deviation (SD), median, 25th percentile, 75th percentile, minimum (min) and maximum (max), for those participants with data. The 25th and 75th percentiles will only be presented when the denominator is at least 10 participants.

For qualitative variables, the number (n) and percentage (%) of participants with non-missing data per category will be the default summary presentation, and where appropriate and present, the number of missing values as a “Missing” category. The number of participants in the analysis population will be used as the denominator for percentages calculation, unless stated otherwise in TFLs mock shell(s).

All statistical comparisons will be made using two-sided tests at the $\alpha=0.05$ significance level unless specifically stated otherwise. All null hypotheses will be of no treatment difference. All alternative hypotheses will be two-sided.

All laboratory test results will be received from central laboratories, and the results will be provided in both standard internal and conventional units. For the TFLs, the results will be summarized or presented in International System of Units (SI) units. Refer to Appendix of the TFLs mock shells for the SI unit corresponding to each laboratory test.

Refer to Appendix of the TFL shells for the precision level in which each laboratory test is reported by the central laboratories.

Specifications for table, figures and data listing formats can be found in the TFL shells specifications for this study. Please refer to “2. General Format Guidelines” section within TFL shells for more details on presentation of results.

In summary tables, participants will be presented by the following treatment groups::

- IM/IM Low Dose
- IM/IM Full Dose
- IM/IV Full Dose

If a participant does not receive a second dose of investigational product they will be assigned to the treatment group IM/IM Full.

In listings, participants will be presented by the following treatment groups:

- Cohort 1: IM/IM Low Dose
- Cohort 2: IM/IM Full Dose
- Cohort 3: IM/IV Full Dose

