7.1 Discontinuation of Trial Intervention

It may be necessary for a participant to permanently discontinue trial intervention. Trial participants who present with at least one of the following VTP-850 discontinuation criteria listed below will be withdrawn from further trial intervention but will remain in the trial to be evaluated for safety, immunogenicity and efficacy, according to their PSA response and SoA ([Section 1.3](#)).

Ulceration, abscess or necrosis at the site of injection of trial VTP-850

Any CTCAE \geq Grade 3 AE considered related to VTP-850 and persisting continuously at \geq Grade 3 for >72 h, with the exception of Grade 3 laboratory test abnormalities that improve to Grade 1 or baseline grade within 14 days

- An SAE considered related to VTP-850
- Acute allergic reaction attributed to the administration of VTP-850

If the participant requests discontinuation of further dosing with VTP-850, it must be documented on the appropriate eCRF and in the medical records whether the participant is discontinuing also from trial procedures, post-intervention trial follow-up, and/or future collection of additional information.

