11.1.2 Analysis sets

- The intent-to-treat analysis set (full analysis set) will consist of all participants who are enrolled into the trial and who received at least one dose of VTP-850
- The safety analysis set will consist of all participants who receive at least one dose of VTP-850 (data will be summarised according to the dose levels and regimens actually received)
- The per-protocol analysis set will consist of all participants in the safety analysis set who received the correct trial intervention and who had no major protocol deviations that would potentially bias the trial's analyses
- The immunogenicity analysis set will consist of all participants who have available immunogenicity data to evaluate the immunogenicity endpoints and do not have any major protocol deviations that would impact the results of the immunological analysis

Assignment of participants to the analysis sets (and whether any participant or specific data from a participant will be excluded) will be determined at the pre-database-lock Data Review meeting.

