4.3. Safety Analysis Set

The Safety Analysis Set (SAF) will consist of all participants who received at least one dose of VTP-850. SAF participants are analyzed according to the dose regimen the participant received.

The SAF will be used for summaries and analysis of demographics and baseline characteristics, treatments and medications, and primary safety endpoints including analyses of adverse events, laboratory safety tests and vital signs.

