4.4. Efficacy Evaluable Set

The Efficacy Evaluable Set (EES) will consist of all participants in the FAS who had one baseline measurement of PSA and at least one post-baseline measurement of PSA. EES participants are analysed according to the dose regimen the participant was allocated.

The EES will be used for analyses of secondary efficacy endpoints which examine PSA response.

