6.6.2. Secondary Efficacy Analysis

6.6.2.1. PSA Response to VTP-850

The number, proportion and 90% confidence intervals (CI) of participants with a confirmed PSA response, defined as a $\geq 50\%$ reduction in serum PSA compared to baseline and measured twice consecutively, at least 2 weeks apart, will be summarized by timepoint (using visit windows defined in Section 5.1) and overall for each treatment group using the EES. The proportion at each time point will present the participants who have the 1st (if confirmed at least 2 weeks later) measurement where the $\geq 50\%$ reduction in serum PSA has been met compared to baseline. Percentage change in PSA will be calculated as $100 \times (\text{PSA value (ng/ml) at visit } i - \text{PSA value at baseline}) / (\text{PSA value at baseline})$. The 90% CIs will be calculated using Jeffrey's confidence limits. The maximum percentage change in PSA from baseline will be summarized continuously by treatment group. A waterfall plot of maximum percentage change in PSA from baseline will be produced by treatment group with bars of the waterfall plot produced using different colours to represent prior radical prostatectomy or definitive external beam radiation (Yes, No). Per cohort, a spaghetti plot will display each participant's percentage change in PSA (e.g. each patient's baseline measurement will display as 100%) by the number of days since the day 1 dosing visit. On each participant's line, a marker will indicate the study day each dose occurred.

Example of this calculation of confirmed PSA response are displayed in Table 7 and Table 8.

Table 7: Calculation of PSA Response Example

Participant	Timepoint	Study Day	PSA Value (ng/mL)	PSA change from baseline	PSA absolute change from nadir	PSA percent change from nadir
1	Baseline	1	1.5			
1	Day 29	29	1.6	6.67%		
1	Day 57	57	1.0	-33.33%		
1	Day 64	64	0.9	-40.00%		
1	Month 4	122	0.8	-46.67%		
1	Month 5	153	0.2	-86.67%		
1	Month 6	164	0.2	-86.67%		
1	Month 7	215	0.3	-80.00%	0.1	50.00%
1	Month 8	246	0.3	-80.00%	0.1	50.00%
1	Month 9	271	0.5	-66.67%	0.3	150.00%

- Responder = Yes
- First observed PSA response = Month 5

- PSA progression (Defined in Section **Error! Reference source not found.**) = Month 9 (since there's a $\geq 25\%$ increase from PSA nadir AND an absolute increase of ≥ 0.2 ng/mL)
- Durable PSA response at Month 8 (Defined in Section 6.6.2.2) = Yes (since a confirmed PSA response has occurred and the criteria for PSA progression has not been met)

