6.7.1. Extent of Exposure

Duration of exposure will be defined in days as:

$$\text{Exposure (days)} = [\text{date of last dose} - \text{date of first dose}] + 1$$

Number and percentage of participant with the following treatment exposure will be calculated:

- 1 ChAdOx1-PCAQ dose only
- 1 ChAdOx1-PCAQ dose + 1 MVA-PCAQ dose
- 1 ChAdOx1-PCAQ dose + 2 MVA-PCAQ doses
- 1 ChAdOx1-PCAQ dose + 3 MVA-PCAQ doses

The number and percentage of participants where the 1st MVA dose was and was not received within the protocol-defined window (Days 27 to 31 from first dose), the 2nd MVA dose was and was not received within the protocol-defined window (Days 55 to 59) and where all planned MVA doses were received within the protocol-defined windows will be presented. Because the timing of the optional third MVA dose is variable depending on when PSA progression occurs, it will not be considered when summarizing timing of the dose relative to protocol windows. Participants whose 2nd dose of MVA was delayed due to study pause will be included in the denominator for 2nd MVA dose (but will be excluded from numerator as dose was received outside protocol-defined window).

Study treatment administration data will be listed for the Safety Analysis Set. The listing will include date/time of administration, the number of days since the previous study dose, the IMP type (ChAdOx1 vs MVA), the route of administration, the planned and total dose and whether the drug was given as per protocol and details if it was not including other specified information.

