- The number and percentage of participants who died will be summarized by the primary reason of death.

In the above summaries, participants with more than one TEAE within a particular SOC are counted only once for that SOC. Similarly, participants with more than one TEAE within a particular PT are counted only once for that PT, respectively. Overall summaries of “Any TEAE” and “Any study treatment-related TEAE” will only include participants at the maximum severity.

For summaries by maximum severity, participants with multiple TEAEs within a particular SOC or PT will be counted under the category of their most severe TEAE within that SOC or PT. TEAEs with missing severity will be included in the counts of the ‘Number of Participants with at least one TEAE’, ‘System Organ Class’ and ‘Preferred Term’ rows of the summary but they will not be included in the counts by severity.

The following tables will also be presented by administration (i.e. ChAdOx1-PCAQ dose, 1st MVA-PCAQ dose, 2nd MVA-PCAQ dose, 3rd MVA-PCAQ dose), for TEAEs that start within 28 days of each administration (e.g. summarizing TEAEs which occurred from ChAdOx1-PCAQ dose up to the earliest of 1st MVA-PCAQ dose or 28 days following the first dose). The denominator will be the number of participants who have received that dose:

- TEAEs
- TEAEs by Maximum Severity
- Treatment-related TEAEs
- Treatment-related TEAEs by Maximum Severity
- Serious TEAEs
- Study Treatment Related Serious TEAEs

Summaries by SOCs and PTs will be sorted by SOCs alphabetically (MedDRA) and PTs within SOC by descending order of total incidence. Where preferred terms tie, PTs will be sorted alphabetically.

No statistical comparisons of AEs between treatment groups will be performed.

All AE data will be listed using the Safety Analysis Set. Treatment-emergence status will be flagged in the listing. The listing will present the relative start and stop day of the AE calculated relative to the first dose of treatment. If the AE is “Ongoing” it will be indicated as such in the listing and the relative stop day will not be calculated.

In addition, the following listings will be presented:

- Listing of Deaths
- Listing of Serious TEAEs
- Listing of AEs Leading to Discontinuation of Study Treatment

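### SAP 6.1 moves every participant without a second dose to IM/IM Full; this contradicts the SAP's own grouping rules for prime-only Cohort 1 participants and, in the PSA and disposition tables, does not fit prime-only Cohort 3 participants

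*SAP*

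**What the plan says.** SAP 6.1 names three treatment groups for summary tables (IM/IM Low Dose, IM/IM Full Dose, IM/IV Full Dose) and then adds: "If a participant does not receive a second dose of investigational product they will be assigned to the treatment group IM/IM Full". Listings use the cohort labels instead.

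The grouping basis for each analysis set is given elsewhere:

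- Safety set, SAP 4.3: "SAF participants are analyzed according to the dose regimen the participant received". Protocol 11.1.2 agrees: "data will be summarised according to the dose levels and regimens actually received".
- Efficacy evaluable set (EES), SAP 4.4: "EES participants are analysed according to the dose regimen the participant was allocated". SAP 6.6.2.1 uses this set for PSA response, which "will be summarized by timepoint (using visit windows defined in Section 5.1) and overall for each treatment group using the EES".

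SAP Table 2 gives the prime as 5×10^9 vp IM in Cohort 1 and 2.5×10^10 vp IM in Cohorts 2 and 3. The booster is IM in Cohorts 1 and 2 and IV in Cohort 3.

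The plan allows for prime-only participants. SAP 6.7.1 has an exposure category "1 ChAdOx1-PCAQ dose only", and under Protocol 7.1 those who meet a discontinuation criterion "will be withdrawn from further trial intervention but will remain in the trial to be evaluated for safety, immunogenicity and efficacy".

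**The concern.** The rule in SAP 6.1 is explicit and unconditional, and it gives a different answer from the set-specific rules in SAP 4.3 and 4.4. A programmer would face two instructions for the same participant, and nothing says which prevails.

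Descriptive tables by group are the main output of Phase 1. A participant who stops after the prime may have stopped because of toxicity, so the dose column in which his events appear matters to anyone reading the safety tables by dose. For PSA response, the question is whether he counts in the denominator of the regimen to which he was allocated.

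**Working it through.** **1. Whom the rule reaches.** The visit-window tables in SAP 5.1.4 tie the Day 29 visit to the second dose of treatment. A participant without a second dose has therefore had the prime only.

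**2. Where he belongs, by cohort and grouping basis.** Prime ratio, Cohort 1 to Cohorts 2 and 3: 5×10^9 / 2.5×10^10 = 0.2.

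| Prime-only participant in | As allocated (EES) | As received (safety set) | IM/IM Full under SAP 6.1 |
|---|---|---|---|
| Cohort 1 | IM/IM Low | low prime, one fifth of full | wrong on both bases |
| Cohort 2 | IM/IM Full | full prime | correct |
| Cohort 3 | IM/IV Full | full prime, no IV dose given | wrong as allocated; defensible as received |

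**3. Whether he can reach the tables.** One dose is enough for the safety set. The EES adds only a baseline and one post-baseline PSA (SAP 4.4). Protocol 7.1 keeps participants who stop dosing under follow-up for efficacy, and the PSA windows from Day 91 onward run from the first dose, so he can enter the EES.

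**4. Which tables are affected.**

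- Cohort 1: all tables by treatment group in which he appears, including exposure, the overall adverse event (AE) tables, the AE table for the ChAdOx1-PCAQ dose, and PSA response. In that ChAdOx1-PCAQ table the IM/IM Full column would mix two prime doses. In the exposure table the prime-only row for Low Dose would be zero by construction.
- Cohort 3: the PSA tables on the EES. The disposition table (SAP 6.2) also fits badly, because its count of participants assigned to treatment rests on the cohort assigned.
- Not affected: the AE tables for the MVA-PCAQ doses, whose denominators contain only those who received that dose (SAP 6.7.2); the per-protocol set, which requires all planned doses; the protocol-deviation tables and the PSA spaghetti plot, both by cohort; the listings; and all overall columns.

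**5. Effect of one moved participant.** Let the column he leaves have n participants and k events, and the column he joins have m participants and j events.

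- Column left, if he had the event: k/n becomes (k−1)/(n−1), a change of (n−k)/[n(n−1)], largest at k=1. If he did not: k/n becomes k/(n−1), a change of k/[n(n−1)], largest at k=n−1. The maximum is 1/n either way. At n=6 it is 1/6 = 16.7 percentage points.
- Column joined: j/m becomes (j+1)/(m+1) or j/(m+1). The maximum is 1/(m+1). At m=6 it is 1/7 = 14.3 points.
- The minimum is 0 in both cases, and the direction depends on whether he had the event.

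The sizes n=6 and m=6 follow the cohort targets in SAP Table 2 and serve as illustrations.

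**6. Illustration for PSA response**, with the 90% Jeffreys interval that SAP 6.6.2.1 specifies. The documents give no counts, so I assume seven Cohort 3 participants in the EES, one of them a prime-only non-responder, and one responder in each group. Cohort 3 as allocated is 1/7 = 14.3% (2.6 to 44.0). Under SAP 6.1 it becomes 1/6 = 16.7% (3.0 to 49.5). With six of its own in the EES, IM/IM Full moves the opposite way, from 1/6 to 1/7.

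**The case against.** The strongest reply is that the sentence has a narrower purpose. Without a booster there is no route to separate IM/IM Full from IM/IV Full, and the sentence may simply settle that case for participants given the full prime. This is plausible, and it is why the Cohort 3 placement is defensible in the safety tables. The text does not state that limit, however. The reading also offers nothing for Cohort 1, where no such ambiguity exists, or for the EES, which follows allocation.

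The second reply is that little depends on it, and much of this stands. SAP 6.7.2 says "No statistical comparisons of AEs between treatment groups will be performed", and SAP 3.1.6 plans no formal hypothesis test. The Safety Monitoring Committee chooses the Phase 2 regimen from its own review of cumulative safety data (Protocol 4.1.1). The Phase 1 participants in the Stage 1 response count are those dosed according to schedule (Protocol 4.1.2). The cohort can be recovered from the listings.

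A reader might infer more than the documents support:

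- *That several participants are affected.* About 25 enrolled, less 12 completers in Cohorts 2 and 3, less 3 to 6 in Cohort 1, leaves 7 to 10. That is planning arithmetic on targets and an approximate total. The remainder could include Cohort 2 participants, who are placed correctly; participants whose second MVA dose was delayed, who have had a second dose; and any never dosed. The exposure category shows that prime-only cases were allowed for. It does not show that one occurred.
- *That the gap between two columns could move by 47.6 points* (1/3 + 1/7). This needs a Low Dose column of three in which he alone had the event, and an IM/IM Full column of exactly six with none (or the mirror image). Replaced and delayed participants may well make the columns larger.
- *That a zero in the prime-only exposure row for IM/IV Full is an error.* Treatment summaries use the safety set, where that placement is defensible. Only the Low Dose zero is a defect.

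**Conclusion.** The point holds as a contradiction within the SAP. For a prime-only Cohort 1 participant, SAP 6.1 conflicts with both the as-received rule and the as-allocated rule. For a prime-only Cohort 3 participant, it conflicts with the as-allocated rule in the PSA tables and does not fit the disposition table. No other section limits the sentence.

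The practical size is conditional. If no Cohort 1 or Cohort 3 participant stopped after the prime, no table changes. If one did, the most his move can do is 1/n in the column he leaves and 1/(m+1) in the column he joins, or 16.7 and 14.3 points at six per column. These are upper limits at assumed sizes and do not predict the actual effect. The documents do not support a claim that the regimen choice, the Stage 1 decision or any between-group test would be altered. The sentence is still worth correcting, because the plan provides for these participants and then directs some of them to the wrong column.

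**What to change.** Revise the SAP 6.1 sentence as follows:

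- Limit it to as-received (safety set) tables and to participants whose only dose was the 2.5×10^10 vp prime.
- Keep prime-only Cohort 1 participants in IM/IM Low Dose in all tables.
- Group the EES and disposition tables by allocated cohort.
- Footnote the number of prime-only participants and the cohort to which each was allocated.

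The cost is a change of SAP wording, a footnote, and separate allocated and received group variables in the programming. Trial conduct does not change. The table shells are not among the documents, so any effect on them cannot be checked.

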6.2. Participant Disposition and Data Sets Analyzed

Participant disposition will be summarized by treatment group and overall, where appropriate, for the All Screened Set. The following information will be reported:

- Number of participants for the following categories:
 - Screened,
 - Screen Failure ('Screen Failure' CRF page lists "Eligibility Evaluation was not completed");
- Number and percentage of participants for the following categories:
 - Assigned to treatment (participants who have not screen failed and have a cohort assigned),
 - Treated (Received one or more doses of VTP-850),
 - Not treated,
 - Completed Short-Term Follow-Up,
 - Discontinued Short-Term Follow-Up,
 - Reason for discontinuing Short-Term Follow-Up;
- Number and percentage of participants included in, and excluded from, each study population together with the reasons for exclusion from the analysis set;
- Number and percentage of participants who completed / did not complete the intervention period, including the reasons for treatment discontinuation (as collected on the End of Treatment CRF page under question "If the participant did not complete the intervention period as per protocol, provide the main reason for discontinuation"), and a summary of number of doses received (ChAdOx1-PCAQ and MVA-PCAQ summarised separately);
- Number and percentage of participants who met / did not meet all eligibility criteria, together with the criteria not met;
- Number and percentage of participants at each site.

A participant will be regarded as having completed Short-Term Follow-Up provided a follow-up visit eCRF page with a nominal visit of either "Month 6" or "End of Treatment" is recorded where a participant status does not equal "Lost to follow-up". For the final analysis, participants missing reason for study completion/discontinuation on an End of Study eCRF form from the question "Reason for study completion/discontinuation" will be considered to have completed the study. For dry run and interim analyses, participants missing reason for

study completion/discontinuation on an ‘Disposition – End of Study’ eCRF page will be considered to be ongoing in the study.

A listing of all participants with their treatment and study completion status, including the respective reasons for treatment and study discontinuation, will be presented for the FAS.

A listing of all screen-failed participants with their reasons for screen failure will be presented for the All Screened Set. A separate listing of participants who failed at least one inclusion / exclusion criterion including a text description of the criterion failed will be presented for the All Screened Set.

A listing of all participants, their inclusion in each analysis set and reasons for exclusion from analysis sets, if excluded from an analysis set, will be presented for the All Screened Set.

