| Immunogenicity assessments | | | | | | | | |
| Blood for PBMC assessment ^f | | | | | X | X | | |
| Blood for anti-antigen antibody assessment | | | | | X | X | | |

Abbreviations: AESIs- Adverse Events of Special Interest, d=days, EOT=End of Trial, PBMC=peripheral blood mononuclear cells, PSA=prostate-specific antigen, PSMA=prostate-specific membrane antigen

^a Participants will only have 1 EOT visit at either Months 6 or 24 or earlier in the event of initiation of new therapy (such as ADT) or development of unequivocal metastatic prostate cancer. Participants with no PSA response in the first 6 months will not enter the Long-Term Follow-up Period. Participants with a PSA response through Month 6 will enter the Long-term Follow-up Period.

^b Visits during the Follow-up Periods are from Day 1. Windows are relative to the target date of the visit.

^c If a cardiac event is reported, blood should be taken for an additional assessment of troponin T and the participant should undergo an additional ECG and echocardiogram at the earliest opportunity

^d If troponin T test result is abnormal, a re-test on the following day is required.

^e PSMA scan can be performed at any time for participants who had a positive PSMA scan prior to screening and where a 50% reduction from baseline in PSA is observed.

^fOnly required at sites qualified by Barinthus Biotherapeutics to perform PBMC isolation/processing.

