7.2 Participant Discontinuation/Withdrawal from the Trial

A participant may withdraw from the trial at any time at his own request or may be withdrawn at any time at the discretion of the investigator for safety, behavioural, disease-management (for example, in the case of rapid PSA progression, a participant may need to discontinue the trial to consider other treatment options) or compliance reasons.

At the time of discontinuing from the trial, if possible, an End of Trial visit should be conducted, as shown in the SoA ([Section 1.3](#)).

The participant will be permanently discontinued from the trial intervention and the trial at that time.

If the participant withdraws consent for disclosure of future information, the sponsor may retain and continue to use any data collected before such a withdrawal of consent.

If a participant withdraws from the trial, he may request destruction of any samples taken and not tested, and the investigator must document this in the site trial records.

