7.3 Lost to Follow-up

A participant will be considered lost to follow-up on the date of latest successful contact if he repeatedly fails to return for scheduled visits and is unable to be contacted by the trial site.

The following actions must be taken if a participant fails to return to the clinic for a required trial visit:

The site must attempt to contact the participant and reschedule the missed visit as soon as possible, counsel the participant on the importance of maintaining the assigned visit schedule, and ascertain whether the participant wishes to and/or should continue in the trial.

Before a participant is deemed lost to follow-up, the investigator or designee must make every effort to regain contact with the participant (where possible, 3 telephone calls, and if necessary, a certified letter to the participant's last known mailing address or local equivalent methods).

These contact attempts should be documented in the participant's medical record.

- Should the participant continue to be unreachable, he will be considered to have withdrawn from the trial.

Site personnel, or an independent third party, will attempt to collect the vital status of the participant within legal and ethical boundaries for all participants enrolled, including those who did not get trial intervention. Public sources may be searched for vital status information. If vital status is determined as deceased, this will be documented, and the participant will not be considered lost to follow-up. Sponsor personnel will not be involved in any attempts to collect vital status information.

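### SAP 6.2 can report a man who withdrew before Month 6 as a Short-Term Follow-Up completer, and it turns a blank End of Study reason into study completion

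*SAP*

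**What the plan says.** SAP 6.2 contains two separate completion rules.

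- **Short-Term Follow-Up.** "A participant will be regarded as having completed Short-Term Follow-Up provided a follow-up visit eCRF page with a nominal visit of either" of two names, End of Treatment or Month 6, is on file. The page counts if it "is recorded where a participant status does not equal" lost to follow-up. No minimum study day is set, and no other status disqualifies.
- **Study completion.** At the final analysis, men whose End of Study form gives no reason "will be considered to have completed the study". In dry runs and interim analyses the same blank means the man "will be considered to be ongoing in the study".

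SAP 6.2 also tabulates men who discontinued Short-Term Follow-Up, with reasons, and men who did not complete the intervention period, with reasons. It provides a listing of completion status, "including the respective reasons for treatment and study discontinuation, will be presented for the FAS".

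On exit visits, Protocol 7.2 says: "At the time of discontinuing from the trial, if possible, an End of Trial visit should be conducted". That section covers a participant's own request and investigator decisions for safety, behavioural, disease-management or compliance reasons. Footnote a to Protocol Table 2 adds: "Participants will only have 1 EOT visit at either Months 6 or 24 or earlier in the event of initiation of new therapy" or on unequivocal metastatic disease. The protocol expands EOT as End of Trial, whereas the SAP rule says End of Treatment.

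**The concern.** A completion rule should separate men observed to the end of the period from men who left before it. This one asks only whether a page with a certain name exists. Men who leave early are asked for an exit visit, so the page may exist because a man left, not because he was followed to Month 6.

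The disposition table matters here because little else in the SAP shows length of follow-up. The primary estimand's variable is adverse events to Month 6 (SAP 3.1.3), summarised as simple numbers and proportions (SAP 3.1.6), so shorter observation tends to lower the count. Exposure in SAP 6.7.1 is measured from first to last dose, and the Efficacy Evaluable Set needs only one post-baseline PSA value (SAP 4.4). In a first-in-human trial whose protocol reports a potential cardiac signal, a reader should be able to see from the summary how many men left before Month 6 and why.

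**Working it through.** No stated figure of the plan depends on these rules, so there is none to reproduce. The check applies the rules to each type of exit.

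**1. Short-Term Follow-Up rule against the period definition.** SAP 5.1.3 ends the period at the earliest of 6 months, metastatic disease or new therapy.

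- Lost to follow-up: not a completer, even if a page exists. Correct.
- Left early, no Month 6 or End of Treatment page: not a completer. Correct.
- Early end visit for new therapy or metastatic disease: a completer. This agrees with SAP 5.1.3.
- Left before Month 6 for another reason, attended the exit visit, and the visit is recorded as End of Treatment: a completer. This contradicts SAP 5.1.3.

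In the last case the man may also fit the discontinued row. SAP 6.2 does not define that row or say which takes precedence.

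**2. The page name.** If End of Treatment is a slip for End of Trial, step 1 applies as it stands. SAP 6.2 also uses End of Treatment for the CRF page that records why the intervention period was not completed. If the rule means that page, stopping dosing early could itself satisfy it. The documents do not settle which is meant.

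**3. Missing End of Study reason.** A recorded discontinuation reason stays a study discontinuation. A blank becomes completion at the final analysis, with no check that a final visit took place. SAP 6.1 provides a missing category for qualitative variables, where appropriate, and SAP 6.2 gives no reason to depart from it.

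**4. Possible size.** The number of affected men, k, is not in the documents, so k = 1 to 3 is an assumption. The shift in reported completion is 100 × k/N percentage points.

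- N = 25 (approximate Phase 1 enrolment, SAP 2.3): 1/25 = 4.0, 2/25 = 8.0, 3/25 = 12.0.
- N = 15 (3 + 6 + 6, the smallest planned cohorts in SAP Table 2): 1/15 = 6.7, 2/15 = 13.3, 3/15 = 20.0.
- Within a treatment group of exactly 6: 1/6 = 16.7 per man. Replacements can make Cohorts 2 and 3 larger, which reduces this.

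**5. Month 6 bounds available for a timing test.** SAP Tables 4 and 5 give a protocol window from Day 173 and an analysis window from Day 166. SAP Table 6 gives Day 176 and Day 121. A timing test needs one agreed lower bound.

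**The case against.** The strongest reply is that the gap is narrow and the data remain visible.

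- **Only some early exits are affected.** A reader might infer that early withdrawals in general are reported as completers. The documents do not support that. The same sentence excludes men lost to follow-up, men with no qualifying page are not completers, exits for new therapy or metastatic disease are planned ends, and the exit visit is only sought where possible. How such visits are named in the eCRF is not documented. This stands and limits the point to the one category in step 1.
- **Unreachable men.** A reader might infer that the lost-to-follow-up exclusion also leaks, because Protocol 7.3 says: "Should the participant continue to be unreachable, he will be considered to have withdrawn from the trial". But a man who cannot be reached attends no exit visit, so under the End of Trial reading he has no qualifying page whatever his status. The leak needs the unproven end-of-dosing reading.
- **Discontinuations do not vanish.** A man leaving on Day 60 has not reached the Day 91 visit, so he should still appear as not completing the intervention period, with a reason. Recorded study discontinuation reasons also appear in the listing, and with about 25 men that listing can be read through. This stands, but a listing does not correct a wrong summary row. The intervention-period row does not show men who leave between Day 91 and Month 6. For a blank reason, the listing has nothing to reveal.
- **No result changes.** Membership of the SAF, FAS and EES, adverse event counts and PSA response do not use these completion flags. This stands in full.

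**Conclusion.** The concern holds in limited form. Both rules are explicit and can put wrong entries in the disposition reporting. The first misclassifies men who leave before Month 6 for reasons other than loss to follow-up, new therapy or metastatic disease, provided their exit visit carries the End of Treatment name. The second misclassifies men with a blank End of Study reason, at the final analysis only.

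The number affected is unknown and could be zero. Each such man would move reported completion by about 4 points if 25 men are the denominator, or 6.7 points if 15.

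A reader might go further and infer that the safety or PSA results are biased by these rules. They are not: the rules affect how well a reader can judge completeness of follow-up, not the estimates. The conclusion about the first rule rests on exit visits being filed under the qualifying name, which the eCRF would confirm or refute.

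**What to change.** Revise SAP 6.2 before database lock.

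1. Count as completed only men with a Month 6 visit inside the SAP's Month 6 window, after reconciling the differing bounds in SAP Tables 4 to 6. Imposing Day 173 without that step would class a Day 170 visit as a discontinuation, although Tables 4 and 5 accept it for analysis from Day 166.
2. For men whose dose was delayed by the study pause, use the Additional Month 6 visit named in SAP 2.7. SAP 5.1.4 already assigns their later visits by recorded name instead of by window.
3. Show exits for new therapy or metastatic disease as a separate planned-end category.
4. Class every other earlier exit visit as discontinued, with its reason, so that no man can fall in both rows.
5. Report a missing End of Study reason as missing, not as completed.
6. Reconcile End of Treatment in the SAP with End of Trial in the protocol, and state which eCRF page each term means.

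The cost is a small change of wording and derivation. No new data collection appears necessary, though the eCRF is not among the documents. The reported completion rate may be lower.
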